9.7. Sample Collection and Handling

The actual dates and times of sample collection must be recorded in the CRF or laboratory requisition form. If blood samples are collected via an indwelling cannula, an appropriate amount (1 mL) of serosanguineous fluid slightly greater than the dead space volume of the lock will be removed from the cannula and discarded before each blood sample is taken. After blood sample collection, the cannula will be flushed with 0.9% sodium chloride, United States Pharmacopeia (USP) (or equivalent) or sodium heparin of 10 U/mL and charged with a volume equal to the dead space volume of the lock. If a mandarin (obturator) is used, blood loss due to discard is not expected.

Refer to the Time and Events Schedule for the timing and frequency of all sample collections.

Instructions for the collection, handling, storage, and shipment of samples are found in the Laboratory Manual that will be provided. Collection, handling, storage, and shipment of samples must be under the specified, and where applicable, controlled temperature conditions as indicated in the Laboratory Manual.

10. SUBJECT COMPLETION/DISCONTINUATION OF STUDY TREATMENT/ WITHDRAWAL FROM THE STUDY

10.1. Completion

A subject will be considered to have completed the double-blind phase if he or she has completed assessments at the end of Week 6 (ie, Day 42) of the double-blind phase (end-of-treatment visit).

A subject will be considered to have completed the follow-up phase if he or she has completed assessments at the follow-up visit (ie, the visit Days 49-56).

Subjects who prematurely discontinue study treatment for any reason before completion of the double-blind phase will not be considered to have completed the study.

10.2. Withdrawal From the Study

A subject will be automatically withdrawn from the study for any of the following reasons:

- Lost to follow-up
- Withdrawal of consent
- Death

- Noncompliance with study drug administration (ie, missing either 4 or more consecutive doses of study medication or a total of 8 or more doses during the 6-week period)
- Investigator's impression of noncompliance with background antidepressant therapy
- Discontinuation of study treatment for any reason. A subject's study treatment will be automatically discontinued if:
 - The investigator believes that for safety reasons or tolerability reasons (eg, adverse event) it is in the best interest of the subject to discontinue study treatment
 - The subject becomes pregnant
 - The subject shows signals of acute suicidal ideation with a clear plan at any time during the study; the subject should be referred to appropriate medical/psychiatric care
 - AST and/or ALT exceeds 5 x Upper Limit of Normal (ULN) (confirmed by repeat testing)
 - AST and/or ALT exceeds 3 x ULN and total bilirubin exceeds 1.5 x ULN (confirmed by repeat testing).

If a subject withdraws from the study before the end of the double-blind phase (ie, Day 42), end-of-treatment and follow-up assessments should be obtained.

If a subject is lost to follow-up, every reasonable effort must be made by the study-site personnel to contact the subject and determine the reason for discontinuation/withdrawal. The measures taken to follow-up must be documented.

When a subject withdraws before completing the study, the reason for withdrawal is to be documented in the CRF and in the source document. Study drug assigned to the withdrawn subject may not be assigned to another subject. Subjects who withdraw will not be replaced.

10.3. Withdrawal From the Use of Research Samples

A subject who withdraws from the study will have the following options regarding the optional research samples:

- The collected samples will be retained and used in accordance with the subject's original separate informed consent for optional research samples.
- The subject may withdraw consent for optional research samples, in which case the samples will be destroyed and no further testing will take place. To initiate the sample destruction process, the investigator must notify the sponsor study site contact of withdrawal of consent for the optional research samples and to request sample destruction. The sponsor study site contact will, in turn, contact the biomarker representative to execute sample destruction. If requested, the investigator will receive written confirmation from the sponsor that the samples have been destroyed.

Withdrawal From the Optional Research Samples While Remaining in the Main Study

The subject may withdraw consent for optional research samples while remaining in the study. In such a case, the optional research samples will be destroyed. The sample destruction process will proceed as described above.

Withdrawal From the Use of Samples in Future Research

The subject may withdraw consent for use of samples for future research (refer to Section 16.2.5, Long-Term Retention of Samples for Additional Future Research). In such a case, samples will be destroyed after they are no longer needed for the clinical study. However, if the subject withdraws consent after the study is over, it is possible that the investigator may have already discarded the subject's medical records that link the subject's name to his or her study number. In this case, the subject's samples would no longer be linked to the subject, and it would not be possible to find the subject's samples for destruction. Details of the sample retention for research are presented in the main ICF and in the separate ICF for optional research samples.

11. STATISTICAL METHODS

Statistical analysis will be performed by the sponsor or under the authority of the sponsor. A general description of the statistical methods to be used to analyze the efficacy and safety data is outlined below. Specific details will be provided in the Statistical Analysis Plan (SAP).

11.1. Subject Information

The efficacy analyses will be based on the full analysis set (FAS) which consists of all subjects who were randomly assigned to study drug and received at least 1 dose of study drug.

Safety analyses will be based on the safety analysis set, which consists of all subjects who were randomly assigned to study drug and received at least 1 dose of study drug. The safety analysis set is the same as the FAS.

Data for all subjects who have received JNJ-42847922 and have at least 1 evaluable PK sample will be included in the population PK analysis.

For all subjects who are randomly assigned to study drug, descriptive statistics (eg, study completion/withdrawal information, demographic and baseline data) will be provided.

11.2. Sample Size Determination

The calculation of the sample size is based on the primary efficacy endpoint (change from baseline to the end of Week 6 for the MADRS total score). The assumptions for the effect size were based on published literature and the clinically meaningful difference between groups to be detected.

The total sample size is calculated on the basis of the generalized Multiple Comparison Procedure-Modeling (MCP-Mod) test⁴⁵ applied to the placebo and the JNJ-42847922 dose groups at the final analysis. Approximately 280 randomized subjects will provide an average weighted power of approximately 85% depending on the underling true dose-response shape,

assuming a 1-sided significance level of 0.05, a treatment difference from placebo of 4.5 points in change in MADRS total score, a standard deviation of 10, and a 25% overall dropout rate.

The data cutoff for the unblinded interim analysis will be 6 weeks after randomization of 160 subjects, which corresponds to approximately 57% of the sample size of the study. This number of subjects provides approximately 93% power to detect a dose-response relationship, depending on the underlying true dose-response shape, assuming a treatment difference of 4.5, and a standard deviation of 10 when tested by means of the MCP-Mod approach at the 30% significance level (1-sided).

11.3. Efficacy Analyses

Primary estimand

The primary estimand, the main clinical quantity of interest to be estimated in the study, is defined by the following 3 components:

Population: subjects with MDD who have had an inadequate response to current antidepressant therapy with an SSRI/SNRI.

Endpoint: change in MADRS total score from baseline to the end of Week 6.

Measure of Intervention: the effect of the initially randomized treatment together with the oral SSRI/SNRI antidepressant that would have been observed had all subjects remained on their treatment throughout the double-blind phase.

The primary analysis will be based on the FAS and the MADRS total scores collected during the double-blind phase.

The primary efficacy endpoint will be evaluated at a 1-sided significance level of 0.05 using the MCP-Mod approach to test for dose-response. For all other analyses of the primary efficacy endpoint and for all other efficacy endpoints, no multiplicity adjustment will be done and nominal 1-sided p-values will be presented.

Primary efficacy endpoint

The primary efficacy endpoint is the change in MADRS total score from baseline to the end of Week 6. A mixed model for repeated measures (MMRM) analysis of the observed data from the placebo and JNJ-42847922 groups will be used as the method of addressing missing data. The MMRM will include region, time, treatment (placebo and JNJ-42847922 dose groups), baseline insomnia status (present/absent), and treatment-by-time interaction as factors and baseline MADRS total score as a covariate. An unstructured variance-covariance matrix will be used. Subjects in the FAS who do not have complete data will still contribute to the estimates at the end of Week 6, but will have less weight in the analysis than those subjects with complete data. The final analysis will use the generalized MCP-Mod approach⁴⁵ (a hybrid methodology that combines multiple comparison procedures with modeling techniques), which will be applied towards estimates obtained from the MMRM analysis to establish a dose-response signal and to

determine dose(s) to be used in the Phase 3 studies. MCP-Mod has been qualified by the European Medicines Agency. ¹⁰

In conjunction, the comparison between JNJ-42847922 and placebo will also be performed using the appropriate contrasts directly from the MMRM analysis using estimates at the end of Week 6.

Secondary efficacy endpoints

Any secondary efficacy endpoint which is defined as a change from baseline will be analyzed using the same MMRM as for the primary efficacy endpoint, with the corresponding baseline as a covariate. Frequency distributions will be provided for CGI-S, PGI-S, and for the number of responders and remitters.

The correlation between baseline ISI score as a continuous variable and change from baseline to the end of Week 6 in the MADRS total score will be evaluated by means of a scatter plot and if appropriate, regression analysis. In addition, subjects will be dichotomized based on their baseline ISI score (≥15 versus <15) to evaluate whether there are differences in these subgroups (ie, evaluating change from baseline to the end of Week 6 in the MADRS total score in subjects with ISI score ≥15 versus subjects with ISI score <15). The shift in ISI score category (score 0-7=no clinically significant insomnia; score 8-14=sub-threshold insomnia; score 15-21=moderate insomnia, and score 22-28=clinically severe insomnia) from baseline to the end of Week 6 will be presented.

Subjects will also be dichotomized based on whether they have MDD with anxious distress or MDD without anxious distress to evaluate whether there are differences in these subgroups (ie, evaluating change from baseline to the end of Week 6 in the MADRS total score in subjects with and without anxious distress).

The secondary endpoint analyses will not be controlled for Type I error and nominal p-values will be presented.

The analyses for the other secondary and exploratory efficacy endpoints will be described in the SAP.

11.4. Pharmacokinetic Analyses

Plasma concentrations for JNJ-42847922, M12, and M16 (if applicable) will be analyzed and summarized by dose, day and time point, using descriptive statistics. A population based PK analysis using PK data from a selection of Phase 1 and Phase 2 studies will be performed at the completion of the study and at the interim analysis. Post-hoc Bayesian estimates of PK parameters for JNJ-42847922 (and, if necessary, for metabolites M12 and M16) from the population PK analysis may be used for exploratory exposure-response analyses.

Population PK analysis of plasma concentration-time data of JNJ-42847922 will be performed using nonlinear mixed-effects modeling. Data may be combined with those of other selected studies to support a relevant structural model. Available baseline subject characteristics

(demographics, laboratory variables, genotypes, race, etc.) will be included in the model as necessary. Post-hoc Bayesian individual estimates of PK parameters will be generated from the population PK analysis for potential use in exposure-response analysis. An interim population PK and exposure-response analysis will be conducted. A snapshot date for PK samples to be analyzed will be defined, if required. Samples collected before this date will be analyzed for JNJ-42847922, M12, and M16 (if applicable) and included in the population PK analysis. Samples collected after the snapshot date will be analyzed at a later date, and may be included in a population PK re-analysis when they become available after database lock. Details for the population PK and exposure-response analysis will be described in a standalone analysis plan and the results of the population PK and exposure-response analysis will be presented in a separate report.

Data will be listed for all subjects with available plasma concentrations per treatment group. Subjects will be excluded from the PK analysis if their data do not allow for accurate assessment of the PK (eg, incomplete administration of the study drug; missing information of dosing and sampling times; concentration data not sufficient for PK parameter calculation).

All concentrations below the lowest quantifiable concentration or missing data will be labeled as such in the concentration database. All subjects and samples excluded from the analysis will be clearly documented in the study report.

For each treatment group, descriptive statistics will be calculated for all individual derived PK parameters including exposure information of JNJ-42847922 and, if needed, M12, and M16.

11.5. Biomarker Analysis

Cortisol levels will be tabulated for each time point and summary statistics will be calculated. Posttreatment changes in cortisol levels will be assessed by treatment group. Analysis of variance (ANOVA) and t-test will be used to assess differences across groups and time points. Correlations between cortisol levels and clinical endpoints will be evaluated.

The additional exploratory biomarkers will be tabulated by treatment and summary statistics will be calculated. Posttreatment changes in exploratory biomarkers will be summarized by treatment group. Associations between baseline biomarker levels and clinical endpoints may be explored. Additional exploratory analyses may also be performed. Results of all exploratory analysis will be presented in a separate report.

All biomarker data obtained from this study may also be included in an ongoing cross-study analysis to investigate the relationship between depression severity, phenotypes, and biomarkers.

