- h. The clinical laboratory assessments (including TSH, hematology, serum chemistry, HbA1c, lipid panel, and urinalysis) should be performed under fasting conditions (with the possible exception of screening laboratory tests).
- i. FT₄ analysis will be performed for subjects with known hypothyroidism who have been on stable treatment for at least 3 months prior to screening and otherwise for any subject with an elevated TSH.
- j. A urine sample will be collected and sent to the central laboratory to assess compliance with the following background antidepressant medications: citalopram, escitalopram, fluvoxamine, fluoxetine, paroxetine, sertraline, and venlafaxine. All other SSRI/SNRI background antidepressants qualifying the subject for enrollment will be assayed (urine or blood sample) locally at the study site, if possible.
- k. Subjects will administer the assigned study drug once daily at bedtime, approximately 3 hours after the last meal, from Day 1 to Day 41. Subjects are required to record the administration of study drug or any missed doses in subject diaries, which will be checked at each scheduled visit.
- 1. As this is a blinded study, blood samples for PK will be collected from placebo-dosed subjects, but not analyzed for PK. These samples will be stored and may be analyzed if needed (eg, suspicion of an incorrect dose).
- m. Pharmacogenomic and epigenetic blood samples will be collected only from subjects who have consented to provide optional DNA samples for research.
- n. To avoid interference caused by lipid content in morning blood specimens collected for biomarker evaluation, biomarker samples will be collected under fasting conditions.
- o. Start date (first day) of last menstrual period and average length of menstrual cycle (days) will be collected from premenopausal women.
- p. Salivary cortisol samples (morning and evening) will be collected by subjects at home. Evening salivary cortisol samples (ie, on Days -1, 7, 21, and 41) will be collected predose, at bedtime. The morning sample will be collected upon awakening (ie, on Days 1, 8, 22, and 42). Subjects should not consume alcoholic beverages for at least 12 hours prior to saliva sampling. Food, drinks (except water), and oral care (brushing, flossing, mouthwash) are not permitted 1 hour prior to the saliva collection.

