- Clinical severity	 Change from baseline to the end of Week 6 in the Clinical Global Impression-Severity (CGI-S) score. 	
 Global functioning (work/school, social and family life). 	 Change from baseline to the end of Week 6 in the Sheehan Disability Scale (SDS). 	
To assess the efficacy of JNJ-42847922 compared to placebo as adjunctive therapy to an antidepressant in improving depressive symptoms in the subpopulation of subjects with MDD with anxious distress.	Change from baseline to the end of Week 6 in the MADRS total score in subjects with MDD with anxious distress versus subjects with MDD without anxious distress.	
To evaluate the effect of JNJ-42847922 exposure on the HPA axis in subjects with MDD.	• Change from baseline to Weeks 2, 4, and 6 in salivary cortisol levels, as measured upon awakening.	

Objectives	Endpoints	
To assess the exposure of JNJ-42847922 and metabolites M12 and M16 in subjects with MDD.	Observed plasma concentrations of JNJ-42847922 and metabolites and estimated exposure parameters for JNJ-42847922 from population based PK modeling.	
To capture patient-reported assessment of JNJ-42847922 compared to placebo as adjunctive therapy to an antidepressant.	 Change from baseline to the end of Week 6 in: Depressive symptoms using the Patient Health Questionnaire 9-item (PHQ-9) Anhedonia using the Snaith-Hamilton Pleasure Scale (SHAPS) Sleep disturbance using the Patient Reported Outcome Measurement Information System-Sleep Disturbance (PROMIS-SD) Short Form Fatigue using the PROMIS-Fatigue Short Form Severity of depression using the Patient Global Impression-Severity (PGI-S) Health related quality of life and utility using the European Quality of Life (EuroQol) Group, 5-Dimension, 5-Level (EQ-5D-5L) questionnaire Work productivity and limitations using the Work Limitations Questionnaire (WLQ) Short Form. 	

In addition, the exploratory objectives are:

- To identify diagnostic biomarkers and to investigate changes in MDD-related biomarkers (HPA axis function, biomarkers of immune system activation and oxidative stress) in relation to clinical response on depression symptoms upon adjunctive treatment with JNJ-42847922
- To explore the exposure/response relationship of JNJ-42847922 in subjects with MDD
- To identify genetic factors that may influence the PK, safety, or tolerability of JNJ-42847922

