#### 1. INTRODUCTION

This statistical analysis plan (SAP) contains definitions of analysis sets, derived variables, and statistical methods for all planned analyses for the clinical study report (CSR) for study 42847922MDD2001.

This SAP does not include planned analyses on biomarkers or pharmacogenomics data or on population pharmacokinetic (PK), pharmacodynamics (PD) and exposure/response analyses, which will be specified as appropriate in separate documents.

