
 
Response of anxiety symptoms
 
	
 
Proportion of responders on anxiety symptoms scale, defined as a ≥50% improvement in the HAM-A total score from baseline to the end of Week 6.
 

 
Clinical severity
 
	
 
Change from baseline to the end o Week 6 in the Clinical Globa Impression-Severity (CGI-S) score.
 

 
Global functioning (work/school, and family life).
 
	social – Change from baseline to the end o Week 6 in the Sheehan Disability Scale (SDS).
• To assess the efficacy of JNJ-428 compared to placebo as adjunctive ther an antidepressant in improving dep symptoms in the subpopulation of st with MDD with anxious distress.	
 
Change from baseline to the end of Week 6 in the MADRS total score in subjects with MDI with anxious distress versus subjects with MDD without anxious distress.
 

• To evaluate the effect of JNJ-428 exposure on the hypothalamic-pituitary-a (HPA) axis in subjects with MDD.	• Change from baseline to Days 8, 22, and 42 in salivary cortisol levels, as measured upon awakening.
• To assess the exposure of JNJ-4284792 metabolites M12 and M16 in subject MDD.	
 
22 and
 
Observed plasma concentrations of JNJ-42847922 and metabolites and estimated exposure parameters for JNJ-42847922 from population based PK modeling.
 

	Objectives		Endpoints	
•	To capture patient-reported assessment JNJ-42847922 compared to placebo	of • as	• C ii	hange from baseline to the end of Week 6
	adjunctive therapy to an antidepressant.		-	Depressive symptoms using the Patient Health Questionnaire 9-item (PHQ-9)
			-	Anhedonia using the Snaith-Hamilton Pleasure Scale (SHAPS)
			_	Sleep disturbance using the Patient Reported Outcome Measurement Information System-Sleep Disturbance (PROMIS-SD) Short Form
			-	Fatigue using the PROMIS-Fatigue Short Form
			-	Severity of depression using the Patient Global Impression-Severity (PGI-S)
			_	Health related quality of life and utility using the European Quality of Life (EuroQol) Group, 5-Dimension, 5-Level (EQ-5D-5L) questionnaire
			_	Work productivity and limitations using the Work Limitations Questionnaire (WLQ) Short Form.

In addition, the exploratory objectives are:

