#### 8. BIOMARKERS

Details of the biomarker analyses are provided in a separate document.

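### The protocol analyses change in awakening cortisol by ANOVA and t-test without a baseline covariate, unlike its rule for secondary efficacy change endpoints; precision is lost and Sections 11.3 and 11.5 need reconciling

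*Protocol*

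**What the plan says.** Protocol 2.1 lists the secondary endpoint as "Change from baseline to Weeks 2, 4, and 6 in salivary cortisol levels, as measured upon awakening". SAP 1.1 has it as "Change from baseline to Days 8, 22, and 42 in salivary cortisol levels, as measured upon awakening". These are the same three visits, since the Time and Events Schedule places Days 8, 22 and 42 in Weeks 2, 4 and 6. Footnote p of that schedule has subjects collect an awakening sample at home on Day 1 and at each of these visits, so a pre-dose baseline exists.

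Protocol 11.5 gives the method, and the Synopsis repeats it: "Posttreatment changes in cortisol levels will be assessed by treatment group", and then "Analysis of variance (ANOVA) and t-test will be used to assess differences across groups and time points". No covariate, stratification factor or within-subject model is named.

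Protocol 11.3 says that secondary efficacy endpoints defined as a change from baseline are analysed "using the same MMRM as for the primary efficacy endpoint, with the corresponding baseline as a covariate". That MMRM also contains region and baseline insomnia status, the two randomization strata.

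The SAP states no cortisol analysis. Its introduction says "This SAP does not include planned analyses on biomarkers or pharmacogenomics data", and Section 8 says "Details of the biomarker analyses are provided in a separate document". SAP Table 4, the list of efficacy variables, does not include cortisol.

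**The concern.** Two sections of one protocol point to different models for a secondary change endpoint. If the Section 11.3 rule covers cortisol, Section 11.5 contradicts it. If it does not, cortisol is the one modelled change endpoint whose stated method leaves out its own baseline, and no reason is given. The SAP adjusts for baseline in every change endpoint that it models: by MMRM for HAM-A, SDS, PHQ-9, SHAPS, both PROMIS scales and MADRS-6, by rank ANCOVA for CGI-S and PGI-S, and by ANCOVA for ISI, which has a single post-baseline visit.

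At stake is the precision of the only endpoint listed for the HPA-axis objective. The Synopsis and Section 1 of the protocol use an earlier morning-cortisol trend as part of the rationale for the drug. A dose-versus-placebo cortisol estimate with wider limits than necessary makes that evidence harder to read, although the baseline sample that would narrow them is already collected.

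**Working it through.** **The plan's own figure.** Neither document states a power, SD, effect or correlation for cortisol. The only stated power is for MADRS in Protocol 11.2: about 85% with 280 randomized, a difference of 4.5, SD 10, 25% dropout and 1-sided 0.05. Evaluable subjects are 280 × 0.75 = 210, which at 2:1:1 is 105 placebo and 52.5 per dose. The MCP-Mod test with the SAP's three candidate shapes then gives 84.4% (linear), 92.7% (emax) and 82.1% (exponential), an average of 86.4%. That agrees with the stated figure, so the same group sizes are used below. They assume that no 10 mg arm is added and that cortisol is missing at the MADRS dropout rate.

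**Precision.** Let s be the cortisol SD, equal at baseline and follow-up, and rho the baseline-to-follow-up correlation. Both are assumptions.

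- Change-score variance per subject: 2(1 − rho)s²
- Baseline-adjusted variance per subject: (1 − rho²)s²
- Ratio, adjusted to change-score: (1 + rho)/2, which is below 1 for any rho below 1

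**Chance imbalance.** The standard error of a baseline difference is √(1/105 + 1/52.5) = 0.169 SD. With no treatment effect, a baseline difference b moves the change-score contrast by (rho − 1)b and a contrast of raw post-baseline levels by rho × b. For b = 0.169 SD:

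| rho | Change-score variance (s²) | Adjusted variance (s²) | Ratio | Shift, change scores (SD) | Shift, raw levels (SD) |
|---|---|---|---|---|---|
| 0.3 | 1.40 | 0.91 | 0.65 | −0.118 | +0.051 |
| 0.5 | 1.00 | 0.75 | 0.75 | −0.085 | +0.085 |
| 0.7 | 0.60 | 0.51 | 0.85 | −0.051 | +0.118 |
| 0.8 | 0.40 | 0.36 | 0.90 | −0.034 | +0.135 |

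The negative sign in the change-score column is over-correction: subtracting the whole baseline removes more than the follow-up value carries forward.

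**Illustration.** Take an assumed effect of 0.4 SD, 105 versus 52.5 subjects and 1-sided 0.05. Adjustment raises power from 63.9% to 79.8% at rho 0.3, from 76.5% to 86.2% at 0.5, from 92.1% to 95.2% at 0.7, and from 98.2% to 98.9% at 0.8.

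**The case against.** The strongest reply is that the operative plan is elsewhere. Section 11 of the protocol calls itself a general description and leaves detail to the SAP. The SAP sends biomarker work to a separate document, and its Amendment 2 log says that the cortisol visit windows went to a biomarker SAP. That document may already adjust for baseline. This stands: what can be criticised is the method the protocol states, not the analysis that will finally be run.

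A second reply is that Section 11.3 already prescribes almost exactly the model wanted here. That stands only in part. The rule is limited to efficacy endpoints, SAP Table 4 leaves cortisol out, and Section 11.5 is the more specific text. The result is an ambiguity to settle.

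Three stronger readings are tempting, and the documents do not support them.

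- A reader might infer that baseline imbalance goes uncorrected. The endpoint is a change, so baseline is already subtracted; what remains is over-correction. Imbalance would be uncorrected only if raw levels were tested, which Section 11.5 does not rule out.
- A reader might infer that repeated samples are treated as independent. The sentence does not say so. Repeated-measures ANOVA and paired t-tests both fit its wording, and a between-arm test at one visit uses one value per subject.
- A reader might infer bias from regression to the mean. Under randomization this affects the arms equally in expectation, so the comparison stays unbiased.

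**Conclusion.** The point holds as one of precision and consistency. The protocol states a less efficient method for a secondary change endpoint than its own rule gives secondary efficacy change endpoints, and it does not say which of the two governs cortisol.

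Over rho 0.8 to 0.3 the avoidable variance is 10% to 35% of the change-score variance. Put the other way, the unadjusted comparison would need 11% (1/0.90) to 54% (1/0.65) more subjects for equal precision. The upper end applies only if awakening cortisol correlates weakly between visits, and the documents do not show whether it does. The figures also rest on equal variances at baseline and follow-up.

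The importance is modest. Secondary analyses carry no Type I error control, the sample size was set on MADRS alone, and the MADRS analysis does not depend on this test. It is still worth changing, because the better method needs no new data.

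**What to change.** Reconcile Protocol 11.3 with 11.5. Replace the ANOVA and t-test sentence in 11.5, and its copy in the Synopsis, with an MMRM of the primary type for change in awakening cortisol:

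- factors: treatment, visit, treatment-by-visit, region and baseline insomnia status;
- covariate: Day 1 awakening cortisol, named explicitly because footnote q of the Time and Events Schedule adds a second pre-dose Day 1 sample taken at the site;
- output: each dose versus placebo, with a confidence interval, at Days 8, 22 and 42.

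Confirm that the separate biomarker SAP specifies the same model. Log transformation is optional; if it is used, the effect becomes a ratio and the endpoint wording should say so.

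The cost is wording and analysis code. No new samples, visits or subjects are needed.
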